16.1.6.3 Other safety measures

Vital signs at each planned assessment and change in vital signs from baseline at each planned post baseline assessment, will be summarised by actual treatment.

Vital signs of PCI will be listed separately.

QT interval will be corrected using Fridericia's (QTcF) formulae.

ECG variables will be summarised by treatment and time point. Differences from baseline will be summarised by treatment and time point.

QTcF > 450 msec and increases in QTcF from baseline (Day 1 predose) of > 30 msec will be considered to be of PCI. The number of subjects with a QTcF value of PCI will be summarised by actual treatment and time point, giving the numbers of subjects with QTcF > 450 msec, > 480 msec and > 500 msec, and the numbers of subjects with increases in QTcF from baseline of > 30 msec and > 60 msec¹³. A supporting listing of all subjects with a QTcF value of PCI, and a separate listing of ECG findings classified as abnormal by the investigator, will also be provided.

Abnormal physical examination findings, (including nasal examination findings) will be listed.

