9.2 Inclusion criteria

1. Healthy male or female volunteer, aged 18–60 years.
2. BMI (Quetelet index) in the range 18.0–30.9 kg/m².

$$\text{Body Mass Index} = \frac{\text{weight [kg]}}{(\text{height [m]})^2}$$

3. Able to understand the nature of the trial and any hazards of participating in it. Ability to communicate satisfactorily with the investigator and to participate in, and comply with the requirements of, the entire trial.
4. Willingness to give written consent to participate after reading the information and consent form, and after having the opportunity to discuss the trial with the investigator or their delegate.
5. Agree to follow the contraception requirements of the trial as described in section 11.
6. Agree not to donate blood or blood products during the study and for up to 3 months after the administration of the trial medication.
7. Spirometry readings (FEV₁ and FVC) to be $\geq 80\%$ of predicted value at the screening visit, calculated using National Health and Nutrition Examination Survey (NHANES) reference. If a subject's FEV₁ or FVC is outside that range at the screening visit, the test may be repeated once on another day.
8. Registered with a General Practitioner (GP) in the UK (Part A only).
9. Willingness to give written consent to have data entered into The Overvolunteering Prevention System (TOPS).

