17. Presence or history of drug or alcohol abuse, or regular intake of more than 14 units of alcohol weekly.
18. Use of cigarettes or nicotine-containing products during the 6 months before first dose of trial medication.

19. Blood pressure and heart rate in supine position at the screening examination outside the ranges: blood pressure 90–140 mm Hg systolic, 40–90 mm Hg diastolic; heart rate 40–100 beats/min. Triplicate measurements will be made (at least 2 min apart), and a mean value outside the above ranges will lead to exclusion.

Repeat measurements (in triplicate) are permitted if values are borderline (ie values that are within 5 mm Hg for blood pressure or 5 beats/min for heart rate) or if requested by the investigator. Subjects can be included if the repeat value is within range or still borderline but deemed not clinically significant by the investigator.

20. QTcF value, of > 450 msec (men) or > 470 msec (women); or QRS duration \geq 120 msec, measured on 12-lead ECG at the screening visit. Triplicate measurements will be made, and a mean value used to determine eligibility. A repeat (in triplicate) is also allowed on one occasion for determination of eligibility.

21. Possibility that the volunteer will not cooperate with the requirements of the protocol.

22. Positive test for hepatitis B surface antigen, hepatitis C or HIV. NOTE: participants with positive hepatitis C antibody owing to resolved disease can be included only if a hepatitis C ribonucleic acid (RNA) test is negative.

23. Positive test for SARS-CoV-2 (polymerase chain reaction; PCR) or suspected exposure to the SARS-CoV-19 virus during the 14 days before screening.

24. Loss of more than 400 mL blood during the 3 months before the trial, eg as a blood donor.

25. Objection by GP to volunteer entering trial.

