12.1 Schedule of procedures

12.1.1 Part A

Period:	Screening 1	Study session											Follow-up			
		Day:	-35 to -2	-1	Pre	0	0.25	0.5	1	2	2.5	3	4	8	12	24
Time (h)																
Informed consent	X															
Inclusion/exclusion criteria	X	X	X													
Medical history	X															
Admission		X														
Inpatient stay			◀											▶		
Discharge																X
Safety assessments																
Physical examination ²	X	X							X							X
Height & weight ³	X	X														X
Vital signs ⁴	X	X	X						X			X	X	X	X	X
12-lead ECG ⁵	X		X							X						X
Serology	X															
Laboratory safety tests ⁶	X	X	X										X		X	X
Pregnancy ⁷	X	X														X
FSH ⁸	X															
Urine drug, alcohol and cotinine tests	X	X														
Spirometry ⁹	X											X	X	X	X	X
Nasal examination	X	X														X
SARS-CoV-2 infection test ¹⁰	X	X														X
Self-assessment nasal tolerability rating scale								X								X
Dosing																
Intranasal Neumifil					X											
Neumifil PK																
PK sampling ¹¹				X					X	X		X				

Abbreviations: ECG: electrocardiogram; FSH: follicle-stimulating hormone; PK: pharmacokinetics; AEs: adverse events.

Notes:

1. Screening will be within 35 days before dosing
2. Full physical examinations will be done at screening and on Day -1. Brief (symptom-directed) physical examinations will be done at all other timepoints.
3. Height measured at screening only.
4. Vital signs consist of: systolic and diastolic blood pressure, heart rate, pulse oximetry, temperature and respiratory rate. They will be assessed at screening; on Day -1, and before and at 2, 4, 8, 12 and 24 h after dosing on Day 1; and at follow-up. Triplicate measurements (at least 2 min apart) will be made at screening and before dosing. Single measurements will be made at all other time points. Measurements should be made with subjects in a supine position, after resting for 5 min.
5. ECGs will be recorded at screening; before and at 2.5 h after dosing on Day 1; and at follow-up. Triplicate recordings (at least 2 min apart) will be made at screening and before dosing; single recordings will be done at all other time points. Recordings should be made with subjects in a supine position, after resting for 5 min.

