If the result of the repeat measurement is still out of range, the investigator will decide on an appropriate course of action.

Standard 12-lead ECGs

12-lead ECGs will be recorded using Mortara ELI250c and ELI280 cardiographs. Each recording will be printed on a single A4 page at paper speed 25 mm/sec and calibrated to 10 mm/mV. Recordings will be made with subjects in a supine position; subjects will remain supine for at least 10 min before the ECG is recorded. PR, RR, QRS and QT intervals will be captured on source documents. QT interval will be corrected using Fridericia's formula (QTcF).

During the trial, if ECG values fall outside the ranges below, a physician will review and decide on an appropriate course of action. The procedure will only be repeated if instructed by a physician.

Ventricular rate:	35–100 beats/min	PR interval:	110–220 msec
QRS:	≤ 120 msec	QTcF (men):	≤ 450 msec
		QTcF (women):	≤ 470 msec

If the result of the repeat measurement is still out of range, the investigator will decide on an appropriate course of action.

Forced expiratory volume test

FEV₁ and FVC will be measured using a CareFusion Micro lab MK8 spirometer.

Nasal examination

At screening, subjects will be asked whether any part of the nose is tender, sore, or irritating, and whether their sense of smell is normal for them. An external

examination of the nose will be done, and significant abnormalities or erythema will be recorded. A nasal speculum will be used to inspect the nose and assess whether nasal polyps, inflammation or erythema are present.

At specified times during the study, subjects will be asked whether any part of the nose is tender, sore, or irritating, and whether their sense of smell has changed since the start of the study. An external examination of the nose will be done, and abnormalities, inflammation or erythema will be recorded, as well as any changes from baseline (screening), or the previous examination. A nasal speculum will be used to inspect the nose and assess whether abnormalities, inflammation, or erythema are present, as well as any changes from baseline (screening) or the previous examination.

Subject self-reported dosing experience

Subjects will complete a self-reported dosing and post-dosing questionnaire. Subjects are asked to assess whether they experienced any of the following using a numerical rating scale from 0 to 10:

- Pain or stinging in the nose
- Burning sensation or sensation of heat/hotness in the nose

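### QTcF > 450 msec is counted as potentially clinically important whatever the sex or baseline, so an eligible woman stable at 451–470 msec normally appears as a case with no change on treatment

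*Combined protocol and SAP*

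**What the plan says.** Section 16.1.6.3 defines the flag: "QTcF > 450 msec and increases in QTcF from baseline (Day 1 predose) of > 30 msec will be considered to be of PCI". It then says how cases are counted: "The number of subjects with a QTcF value of PCI will be summarised by actual treatment and time point". The absolute categories are above 450, 480 and 500 msec; tabulated apart from them are "the numbers of subjects with increases in QTcF from baseline of > 30 msec and > 60 msec". A listing of all subjects with a QTcF value of PCI supports the table. The same section also summarises ECG variables and their differences from baseline by treatment and time point.

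Two other places set QTcF limits, and both depend on sex:

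- **Section 9.3, criterion 20** excludes a "QTcF value, of > 450 msec (men) or > 470 msec (women"), judged on the mean of triplicate screening recordings.
- **Section 12.4, Standard 12-lead ECGs**, says "During the trial, if ECG values fall outside the ranges below, a physician will review and decide on an appropriate course of action". The range given for QTcF is up to 450 msec in men and up to 470 msec in women.

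Both sexes are recruited (section 9.2: "Healthy male or female volunteer, aged 18–60 years").

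**The concern.** The lowest absolute category overlaps the range in which women may enter the trial. A woman at 451–470 msec is acceptable under sections 9.3 and 12.4 but of PCI under section 16.1.6.3 before she has been dosed. She then remains a case without any movement in her QTcF. For her, the > 450 msec count describes who was enrolled and not what happened after dosing.

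This sits awkwardly with the rest of the plan. The primary endpoint is framed as clinically significant changes, including in the ECG (section 7.2.1). A laboratory value is of PCI only if it is both outside the reference interval and moved from baseline by more than a set amount (section 16.1.6.2). A treatment-emergent adverse event must be new or worse (section 16.1.6.1). The absolute QTcF flag has no such condition.

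No hypotheses are tested (section 16.1.2), so the safety conclusions rest on descriptive tables, and the results are meant to inform dose selection in later trials (section 6.3). In groups with 4 or 6 active subjects, one case that reflects entry status is visible.

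**Working it through.** The plan states no figure to reproduce, so the check applies its written rules.

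**1. Rules applied to a QTcF that does not change**

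| Stable QTcF (msec) | Woman eligible (9.3) | Woman in range (12.4) | > 450 msec (16.1.6.3) | Increase > 30 msec |
|---|---|---|---|---|
| 450 | yes | yes | no | no |
| 451 | yes | yes | yes | no |
| 460 | yes | yes | yes | no |
| 470 | yes | yes | yes | no |
| 471 | no | no | yes | no |

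A man with a screening mean above 450 msec is excluded, so the built-in overlap concerns women only.

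**2. How often she is counted.** In Part A (section 12.1.1), "ECGs will be recorded at screening; before and at 2.5 h after dosing on Day 1; and at follow-up": 2 post-dose ECGs. In Part B (section 12.1.2, note 6), the ECGs after the Day 1 predose baseline are 2.5 h on Day 1, predose and 2.5 h on Day 7, and follow-up: 4 ECGs.

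**3. Weight of one subject** (group sizes from sections 8.1.1 and 8.1.2)

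- Active, Groups A1–A3: 1/4 = 25%.
- Active, Groups A4, A5 and B1–B3: 1/6 = 17%.
- Placebo pooled over planned Part A groups: 2 + 2 + 2 + 3 + 3 = 12, so 1/12 = 8%.
- Placebo pooled over planned Part B groups: 2 + 2 + 2 = 6, so 1/6 = 17%.

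Section 16.1.6.3 says only that counts are by actual treatment. It does not say whether placebo is pooled.

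**4. Allowing for reading variability.** The documents give no within-subject SD, so s = 5 to 10 msec is an assumption, with readings treated as independent. For a true stable value m, P(one reading > 450) = 1 − Φ((450 − m)/s), and P(all k readings > 450) is that probability to the power k.

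| m (msec) | One reading, s = 10 to 5 | Both in Part A | All four in Part B |
|---|---|---|---|
| 455 | 0.691 to 0.841 | 0.478 to 0.708 | 0.229 to 0.501 |
| 460 | 0.841 to 0.977 | 0.708 to 0.955 | 0.501 to 0.912 |
| 465 | 0.933 to 0.999 | 0.871 to 0.997 | 0.758 to 0.995 |

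She is therefore usually counted at any given ECG, but not certainly at every one.

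**5. The change category for the same woman.** P(false increase > 30 msec at one reading) = 1 − Φ(30/(s√(1 + 1/n))), where n is the number of recordings averaged for baseline. At s = 10 this is 0.0047 for n = 3 (Part A predose triplicate, if averaged) and 0.017 for n = 1 (Part B single predose recording). The > 30 msec count almost never picks her up; the > 450 msec count usually does.

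**6. Does the word joining the two PCI conditions help?** If PCI required both > 450 msec and an increase > 30 msec, she would not be of PCI. But the section then tabulates absolute values and increases as separate counts, so she would still be in the > 450 msec count.

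**The case against.** The strongest reply is that section 16.1.6.3 already supplies what a reader needs. Differences from baseline, counts above 480 and 500 msec, counts of increases above 30 and 60 msec, and a subject listing are all reported. A stable woman shows a change near zero and falls in neither increase category. This stands, and it limits the point. A reader might infer that one such woman makes a dose level look as if it prolongs QTcF, or hides a signal if she is on placebo. That would require ignoring the rest of the section. Nor does the text rank the > 450 msec count as the main ECG result; it is one of five categories.

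Second, nothing operational depends on the flag. The stopping criteria (sections 8.4.1, 8.4.2 and 9.4.2) do not mention it, escalation rests on the Safety Review Group's review of ECGs among other data (section 8.5.1), and on-study physician review already uses the sex-specific range. This also stands.

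Third, eligibility, physician review and a reporting flag serve different purposes and need not share a limit; a sensitive flag may be intended. That is possible, and the section cites a guideline for its categories, but the protocol does not explain the difference.

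Fourth, aligning the PCI limit with sections 9.3 and 12.4, and dropping subjects already above it at baseline, would lose information. A woman going from 445 to 470 msec (+25) would be neither > 470 msec nor up by more than 30 msec. A man at 452 msec predose who reaches 481 msec (+29) would be removed by the baseline condition. Both are listed under the current text. This objection is sound, and the fix below avoids that route.

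**Conclusion.** The inconsistency is real and follows from the text alone. Section 16.1.6.3 counts any QTcF > 450 msec regardless of sex or baseline, while sections 9.3 and 12.4 accept up to 470 msec in women. One stable woman in that band adds 25% or 17% to an active group's lowest absolute category, or 8% (Part A) or 17% (Part B) to placebo if pooled within part. The damage stops at the > 450 msec count, the PCI total and its listing.

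The number of such women cannot be derived, because the documents give neither the sex mix nor the QTcF distribution. A reader might want an expected number among the planned active subjects (3 × 4 + 2 × 6 + 3 × 6 = 42). Assuming 20–50% women and 5–15% of them at 451–470 msec gives 42 × 0.20 × 0.05 = 0.4 to 42 × 0.50 × 0.15 = 3.2. Both inputs are pure assumption and the range includes the likelihood of none, so the conclusion does not rest on it. A 1/2 placebo rate is also tempting, but it holds only if placebo is tabulated by group in a group with two placebo subjects.

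This is a reporting weakness worth correcting, not a threat to subject safety or to the conduct of the trial.

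**What to change.** In section 16.1.6.3, or in the SAP due before first database lock (section 16.1.1):

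1. Keep the > 450, > 480 and > 500 msec categories, the > 30 and > 60 msec change counts and the PCI listing.
2. Present the absolute categories by treatment as a shift from baseline category to highest post-dose category.
3. Report separately the number of subjects who newly enter a higher category after dosing.
4. Show sex and baseline QTcF in the PCI listing.
5. State whether placebo is pooled within each part.
6. Reconcile the single 450 msec limit with the sex-specific limits in sections 9.3 and 12.4, or state why it differs.

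Under this layout a woman stable at 460 msec stays on the diagonal of the shift table and is not a new entry. The changes from 445 to 470 msec and from 452 to 481 msec both appear as new entries and both stay in the listing. A rise inside one category, such as 455 to 478 msec, does not show as a shift, but the listing still carries it with its baseline.

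The cost is one extra table and two listing columns, with no new data.

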16.1.6.4 Immunogenicity assessment (Part B only)

Analyses of ADAs to Neumifil will be listed and summarised by treatment group and timepoint. This analysis will be reported separately to the clinical study report.

16.1.7 Plasma concentration data analyses

Neumifil plasma concentration data will be listed by treatment and time point.

16.1.8 Pharmacodynamic data analyses (Part B only)

Presence of cytokines and chemokines will be listed and summarised by treatment and timepoint.

PD concentrations at each planned assessment and change in PD concentrations from baseline at each planned post baseline assessment, will be summarised by actual treatment.

16.2 Determination of sample size

Since this is a pilot trial, no formal sample size determination is appropriate.

17 Ethical and regulatory requirements

The trial proposal will be reviewed by a recognised REC, and by the MHRA. The trial will not proceed unless the sponsor obtains from the MHRA a clinical trial authorisation (CTA), and the REC gives a favourable opinion of the trial.

The trial will be done at HMR, in compliance with The Medicines for Human Use (Clinical Trials) Regulations 2004 and current amendments¹⁵, The Medicines for Human Use (Clinical Trials) (Amendment) (EU Exit) Regulations 2019¹⁶, The

Human Medicines (Amendment etc) (EU Exit) Regulations of 2019 and 2020^{17,18}, GMP¹¹, the SOPs issued by RES for RECs in the UK¹⁹, and Good Clinical Practice, which has its origins in the Declaration of Helsinki.

All subjects must give written consent to participate in this trial. Consent for screening evaluations may be obtained using the information and consent form for the HMR healthy volunteer panel, which has been approved by the Health Research Authority's Generic Document Review Committee. The trial specific information and consent form will be signed by the subject either before any screening evaluation or after the investigator confirms the eligibility of the subject for the trial and before the subject is randomised to receive the first administration of IMP. Before giving consent, subjects must read the information sheet about the trial. They must also read the consent form. They will then discuss the trial with the investigator or his deputy and be given the opportunity to ask questions. The trial-specific information sheet and the consent form must be approved by the REC.

Each subject is free to withdraw from the trial at any time, without giving a reason. If a subject withdraws, the investigator will ask the subject to consent to a follow-up examination. For withdrawn subjects, the investigator will use a special information and consent form which has been ethically approved. If the subject consents to the follow-up examination but asks the investigator to destroy all identifiable samples taken from the subject and/or not enter into the eCRF results of the follow-up examination, the investigator will comply with the subject's requests.

The sponsor will ensure that the MHRA and the REC, are informed promptly of SUSARs (see section 14.3), and that any new reports of SUSARs from other ongoing trials of the IMPs under investigation in this trial are notified to the MHRA, and to the REC, if applicable. The sponsor will provide the investigator, the REC and the MHRA with annual safety reports of the IMP under investigation, and listings of all suspected serious adverse reaction (SSAR) reports. The sponsor will also inform the investigator promptly of any new safety or toxicology data that might affect the safety of the subjects in this study.

The investigator will promptly inform the sponsor and, if applicable, the REC of any SAE that occurs during this trial (see section 14.3). The investigator will provide the REC with annual progress reports of the trial, if the trial lasts longer than a year.

The investigator will report to the REC any protocol deviation that is, in his opinion, of clinical significance. The investigator will also inform the REC in the event of several deviations which, although of no clinical significance, cause inconvenience and/or discomfort to the volunteers. The sponsor will notify the MHRA and REC of any serious breach of good clinical practice (for example, the investigator puts subjects' safety at risk, falsifies data, or persistently fails to comply with this protocol or good clinical practice).

Within 90 days after the end of the trial, the sponsor (or sponsor's delegate) will ensure that the REC and the MHRA are notified that the trial has finished. If the trial

is terminated prematurely, those reports will be made within 15 days after the end of the trial.

The sponsor will supply a summary of the clinical trial report to the MHRA and REC within 1 year after the end of the trial.

Trial procedures at HMR will be subject to audits by the HMR QA Department, to ensure compliance with the protocol and applicable regulatory requirements.

18 Trial documentation

18.1 Protocol amendments

After the protocol has been approved by the REC and the MHRA, no changes may be made without the agreement of both the investigator and the sponsor.

The MHRA and REC do not need to approve any substantial change to the protocol that needs to be implemented urgently to avoid an immediate hazard to trial subjects. The sponsor will ensure that the MHRA and REC are informed of urgent amendments in accordance with The Medicines for Human Use (Clinical Trials) Regulations 2004 and current amendments¹⁵ and the SOPs issued by RES for NHS RECs¹⁵.

All agreed protocol amendments will be recorded on a written agreement which will be signed and dated by the investigator and sponsor, and attached to the original protocol. The REC and/or MHRA must approve substantial amendments before they are implemented.

The standard text in our information and consent form template explains that the planned doses may change during the trial, and that we may give the subjects any dose that has been approved by the MHRA and REC for the trial. However, if we want to reduce the planned dose, we consider it essential to fully inform the subject of our reasons, because a reduction in dose might be due to poor tolerability, and that might affect the subject's decision to remain in the trial. Wherever possible, we will obtain prior approval from the REC for the information and consent form that we give to subjects before we reduce the dose. But, owing to the nature of trials on healthy volunteers, it is likely that we will sometimes have to implement an urgent amendment to lower the planned dose, to avoid immediate hazard to the subjects. We will fully inform the subjects of the reason for reducing the dose and will notify the REC and MHRA promptly of the urgent amendment, in accordance with statutory requirements.

